6. RATIONALE AND BACKGROUND

Azathioprine is a purine analogue and prodrug of mercaptopurine that is used as an immunosuppressive medication alone or in combination with other immunosuppressive therapy to prevent rejection following organ transplantation and to treat certain autoimmune diseases, where it is considered a steroid-sparing agent. Examples of autoimmune diseases that could be treated with azathioprine are rheumatoid arthritis, inflammatory bowel disease, systemic lupus erythematosus (SLE), polymyositis, dermatomyositis, multiple sclerosis (MS) and myasthenia gravis(1-7).

Azathioprine is associated with minor usually transient and asymptomatic elevations of aminotransferase levels and with rare instances of acute cholestatic liver injury and with long-term use, portal hypertension may occur(8, 9).

A signal procedure regarding a potential association between azathioprine and non-cirrhotic portal hypertension/portosinusoidal vascular disease (PSVD) - which is a rare disorder characterised by signs of portal hypertension in the absence of an identifiable aetiology, such as cirrhosis - is needed. A liver biopsy is mandatory for the diagnosis of PSVD.(10) Specific histologic signs include obliterative portal venopathy, nodular regenerative hyperplasia and incomplete septal fibrosis (10).

This study is intended to support the signal evaluation by providing information about the use of azathioprine, including the most frequent indications, the age- and sex distribution at initiation of treatment, and the treatment duration for all indications combined, and for each indication separately.

	D2.2.3 - Study Protocol for P3-C1-014	
	Author(s): [name], [name]	Version: V4.0
	Dissemination level: Public	

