7. RESEARCH QUESTION AND OBJECTIVES

The aim of this study is to characterise individuals treated with Azathioprine.

The specific study objectives are:

1. Characterise azathioprine initiators by sex and age at first prescription, overall and per indication
2. Identify potential indications for azathioprine, and the percentage of azathioprine-treated patients for each pre-defined approved indication:
 - a) Organ transplantation
 - b) Severe rheumatoid arthritis or chronic polyarthritis
 - c) Inflammatory bowel disease
 - d) Autoimmune hepatitis
 - e) Systemic lupus erythematosus
 - f) Dermatomyositis
 - g) Polyarteritis nodosa
 - h) Pemphigus vulgaris and bullous pemphigoid
 - i) Behçet's disease
 - j) Refractory autoimmune haemolytic anaemia
 - k) Refractory idiopathic thrombocytopenic purpura
 - l) Polymyositis
 - m) Pyoderma gangrenosum
 - n) Multiple sclerosis
 - o) Myasthenia gravis
 - p) None of the above/missing
3. Large-scale characterisation overall and per indication of drugs and conditions within one year prior to the index date (-365 to -1 day to the index date) and on the index date will be assessed.
4. Estimate and summarise duration of treatment with azathioprine, overall, and stratified per indication

Description of the proposed objectives are described in ([Table 1](#)).

Table 1. Primary and secondary research questions and objective.

A. Primary research question and objective.

Objective 1,2,3 and 4:	To characterise individuals newly treated with Azathioprine by age and sex. In addition, new users of Azathioprine will be characterised in terms of indication and treatment of use. Characterisation will be done in terms of demographics, indication, treatment duration and prior drug use and comorbidities
Hypothesis:	N/A
Population (mention key inclusion-exclusion criteria):	All patients present in the databases with at least 365 days of prior history and newly treated with Azathioprine
Exposure:	Exposure to Azathioprine

	D2.2.3 - Study Protocol for P3-C1-014	
	Author(s): [name], [name]	Version: V4.0
	Dissemination level: Public	

Comparator:	N/A
Outcome:	N/A

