8.5 Study population with inclusion and exclusion criteria

The study population will include all individuals observed in one of the participating data sources during the study period (1st January 2000 to 31st December 2023) and having at least 1 year of database history.

Patients will be excluded if the start date in the database falls within 365 days prior to the index date, as sufficient data availability is required.

The operational definitions of the inclusion and exclusion criteria are presented by means of **Table 5** and **Table 6** , respectively.

	D2.2.3 - Study Protocol for P3-C1-014	
	Author(s): [name], [name]	Version: V4.0
	Dissemination level: Public	

Table 5. Operational definitions of inclusion criteria.

Criterion	Details	Order of application	Assessment window	Care Settings ¹	Code Type	Diagnosis position ²	Applied to study populations:
Prior database history	Study participants will be required to have 365 days of prior history observed before the index date	Prior	[-365,-1]	OP	N/A	N/A	All individuals within selected databases
Observation period in the database during the period	All individuals present in the 2000-2023 (or the latest date available)	after	N/A	OP	N/A	N/A	All individuals within selected databases
User of Azathioprine (exposure)	Prescription record of azathioprine	after	Study period	OP	RxNorm	N/A	All individuals within selected databases

¹ IP = inpatient, OP = outpatient, ED = emergency department, OT = other, n/a = not applicable

² Specify whether a diagnosis code is required to be in the primary position (main reason for encounter)

	D2.2.3 - Study Protocol for P3-C1-014	
	Author(s): [name], [name]	Version: V4.0
	Dissemination level: Public	

Table 6. Operational definitions of exclusion criteria.

Criterion	Details	Order of application	Assessment window	Care Settings ¹	Code Type	Diagnosis position ²	Applied to study populations:	Measurement characteristics/validation	Source for algorithm
N/A	N/A	N/A	N/A	N/A	N/A	N/A	N/A	N/A	N/A

¹ IP = inpatient, OP = outpatient, ED = emergency department, OT = other, n/a = not applicable

² Specify whether a diagnosis code is required to be in the primary position (main reason for encounter)

	D2.2.3 - Study Protocol for P3-C1-014	
	Author(s): [name], [name]	Version: V4.0
		Dissemination level: Public

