8.6.1 Exposure/s

Azathioprine exposure consists of a prescription record of azathioprine (for systemic use thus oral or parenteral use). The operational definition of exposure is described by means of **Table 7**.

	D2.2.3 - Study Protocol for P3-C1-014	
	Author(s): [name], [name]	Version: V4.0
	Dissemination level: Public	

Table 7. Operational definitions of exposure.

Exposure group name(s)	Details	Washout window	Assessment Window	Care Setting ¹	Code Type	Diagnosis position ²	Applied to study populations	Incident with respect to...	Measurement characteristic s/ validation	Source of algorithm
Azathioprine	Preliminary code lists provided in Appendix I	[-inf,-1], for incident use only	Anytime post start of the study date	OP	RxNorm	N/A	All eligible individuals in the database	Azathioprine use	N/A	N/A
Azathioprine + indication of use	Preliminary code lists provided in Appendix I	n/a = not applicable	Indication of use in - 90/+30 days of index date	OP	SNOMED codes to assess indication of use	Yes (indication of use)	All incident users of azathioprine	Azathioprine use	N/A	N/A

¹ IP = inpatient, OP = outpatient, ED = emergency department, OT = other, n/a = not applicable

² Specify whether a diagnosis code is required to be in the primary position (main reason for encounter)

	D2.2.3 - Study Protocol for P3-C1-014	
	Author(s): [name], [name]	Version: V4.0
	Dissemination level: Public	

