8.6.3 Other covariates, including confounders, effect modifiers and other variables

The study covariates are described conceptually, and the context or rationale for the choices are provided in this section. The operational definition of the covariates is described in the [Table 9](#).

Covariates for the patient-level characterisation

To characterise the new initiators of Azathioprine, the covariates will include:

- age at the index date (first prescription of Azathioprine) presented as a mean/median age as well as proportion of patient stratified within age groups (<18, 18-44, 45-64, 65-79, and >=80), overall and per indication
- sex (male/ female), overall and per indication.
- Conditions considered indications for Azathioprine use, will be assessed within -90/+30 days of the index date. These indications will be identified based on the presence of disease codes. The preliminary code list for each condition of interest is available in [Appendix I](#).

Indications:

- Organ transplantation
- Severe rheumatoid arthritis or chronic polyarthritis
- Inflammatory bowel diseases
- Autoimmune hepatitis
- Systemic lupus erythematosus
- Dermatomyositis
- Polyarteritis nodosa
- Pemphigus vulgaris and bullous pemphigoid
- Behcet's disease
- Refractory autoimmune haemolytic anaemia
- Refractory idiopathic thrombocytopenic purpura
- Polymyositis

	D2.2.3 - Study Protocol for P3-C1-014	
	Author(s): [name], [name]	Version: V4.0
		Dissemination level: Public

- Pyoderma gangrenosum
 - Multiple sclerosis
 - Myasthenia gravis
 - None of the above/missing
- Large-scale characterisation: overall and per indication of drugs (by RxNorm code at ingredient level) and conditions (by standard SNOMED code) within one year prior to the index date (-365 to -1 day to the index date) and at the index date will be assessed. While all conditions and medications above 1% will be available within the Shiny App, only the 10 most frequent conditions and drugs will be described within the report. Drugs will be reported by ingredient and not by strength or formulation

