 - Treatment duration overall and per indication, will be assessed from the index date until date of: 1) censoring or loss to follow-up, 2) end of data availability, or 3) the end date of exposure (whichever occurs first). Furthermore, to provide more context, also the proportion (%) of patients with a duration that fall within a prespecified treatment duration group will be calculated and provided, both for the overall treatment duration as per indication. The prespecified treatment duration groups will be: <12 months, 12-24 months, 2-3 years, 3-4 years, 4-5 years, 5-10 years and ≥10 years.

	D2.2.3 - Study Protocol for P3-C1-014	
	Author(s): [name], [name]	Version: V4.0
	Dissemination level: Public	

Table 9. Operational definitions of covariates.

Characteristic	Details	Type of variable	Assessment window	Care Settings ¹	Code Type	Diagnosis Position ²	Applied to study populations	Measurement characteristics / validation	Source for algorithm
Demographics	Age and sex at index date	Numeric, continuous, binary	All history	OP	N/A	N/A	Incident azathioprine users	N/A	N/A
Indications	Prespecified indications of interest - 90/+30 days of the index date	Count, binary	[-90, +30]	OP	SNOMED	N/A	Incident azathioprine users	N/A	N/A
Medication use, comorbidities	All history prior to the index date (large-scale characterisation)	Count, binary	[-365, -1] and [0,0]	OP	SNOMED, RxNorm	N/A	Incident Azathioprine users	N/A	N/A
Treatment duration	Duration of treatment with Azathioprine for the: 
 - new users of azathioprine use - New users of azathioprine per indication 	Numeric, continuous	[0, end of exposure]	OP	N/A	N/A	Incident azathioprine users	N/A	N/A

¹ IP = inpatient, OP = outpatient, ED = emergency department, OT = other, n/a = not applicable

² Specify whether a diagnosis code is required to be in the primary position (main reason for encounter)

	D2.2.3 - Study Protocol for P3-C1-014	
	Author(s): [name], [name]	Version: V4.0
		Dissemination level: Public

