11. LIMITATIONS OF THE RESEARCH METHODS

Regarding azathioprine use, the recording of the prescription of the drug (e.g. concept id at clinical drug level or at ingredient level), and the prescriptions themselves may vary across databases. In addition, a recording of a prescription or dispensation does not mean that the patient actually took the drug. In addition, assumptions around the duration of drug use will be unavoidable and might lead to overestimating treatment duration of treatment (considering a 30-day drug gap era).

	D2.2.3 - Study Protocol for P3-C1-014	
	Author(s): [name], [name]	Version: V4.0
		Dissemination level: Public

For this study, the indication of use is important and predefined indications of use have been identified. Not all of these indications of interest might be present within the database (i.e. in DP with less granular source coding such as IPCI). For that reason, it might be interesting to use more broad definitions of the indication of use (e.g. look for “inflammatory disease of liver” and not necessarily “autoimmune hepatitis”. These broad searches might impose a potential of misclassification however, as we search in a relatively small window, 3 months before and 1 month after, around the index date (first prescription of azathioprine during study period) this risk of misclassification is probably minimal. Also, the large-scale characterisation (looking for top 10 disease codes) might provide insight into the indication of use on top of the indications which have been predefined.

The study period is from 2000 until 2023 however not all DPs have that long observation time. For IPCI, observation period starts from 2008 and for SIDIAP from 2005.

Small cell counts may affect the analysis for some subgroup strata. If the numbers are too low, counts will not be disclosed for governance reasons.

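### Indications are searched only from day -90 to day +30, so a chronic disease coded earlier and not re-coded in those 121 days is counted as having no listed indication; Section 11 does not consider this loss

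*Protocol*

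**What the plan says.** Section 8.6.3 sets the window, "Conditions considered indications for Azathioprine use, will be assessed within -90/+30 days of the index date", and the means of detection: "These indications will be identified based on the presence of disease codes". Table 9 repeats it ("Prespecified indications of interest - 90/+30 days of the index date"), and so does Table 7 in Section 8.6.1 ("Indication of use in - 90/+30 days of index date"). No second window appears anywhere, and item 10.8 of the ENCePP checklist, on sensitivity analyses, is marked not applicable.

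The last category in every indication list is 'None of the above/missing'. It holds patients treated for something else together with patients for whom no code was found.

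Section 11 links the short window to the broad code lists and concludes that "around the index date (first prescription of azathioprine during study period) this risk of misclassification is probably minimal". It adds that the large-scale characterisation may give further insight into indication.

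Table 5 fixes the available look-back: "Study participants will be required to have 365 days of prior history observed before the index date".

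**The concern.** Most of the listed indications are chronic: inflammatory bowel disease, rheumatoid arthritis, lupus, multiple sclerosis, myasthenia gravis and others. Section 6 says azathioprine is used "to treat certain autoimmune diseases, where it is considered a steroid-sparing agent", and two indications are labelled refractory. Both leave room for a diagnosis that precedes the first azathioprine prescription by more than 90 days. Such a patient is classified correctly only if the disease happens to be coded again inside the window.

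Section 11 does not address this. Narrowing a window protects against counting an unrelated code as the indication, but it raises the chance of missing the true one. Section 11 weighs the first error and is silent on the second.

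Objective 2 asks for "the percentage of azathioprine-treated patients for each pre-defined approved indication". Missed codes lower those percentages and enlarge the residual category. The per-indication parts of objectives 1, 3 and 4 would then describe only patients coded close to the start of treatment, who may differ in age and treatment duration. Re-coding habits can differ between databases and diseases, so part of any contrast between them could reflect recording practice.

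**Working it through.** The protocol states no expected share with or without an indication, so there is no figure to reproduce.

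**Step 1: window length (Section 8.6.3, Table 9).** Days -90 to +30 including day 0: 90 + 1 + 30 = 121 days.

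**Step 2: guaranteed history not searched (Table 5).** 365 - 90 = 275 days, from day -365 to day -91. The search uses 90/365 = 25% of the look-back that every patient must have. The large-scale characterisation already uses days -365 to -1.

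**Step 3: length of a one-year alternative.** Days -365 to +30: 365 + 1 + 30 = 396 days.

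**Step 4: illustration of capture.** *Assumption, not in the documents:* a patient whose disease has been known for at least a year receives indication codes at a constant rate r per year, independently of the index date. Then

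P(at least one code in a window of d days) = 1 - exp(-r × d/365).

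| r per year (assumed) | [-90,+30], d = 121 | [-365,+30], d = 396 |
|---|---|---|
| 1 | 1 - exp(-0.332) = 28% | 1 - exp(-1.085) = 66% |
| 2 | 1 - exp(-0.663) = 48% | 1 - exp(-2.170) = 89% |
| 4 | 1 - exp(-1.326) = 73% | 1 - exp(-4.340) = 99% |
| 12 | 1 - exp(-3.978) = 98% | 100% (rounded) |

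The loss with the present window therefore runs from 72% of known cases at one code a year to about 2% at monthly coding.

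**Step 5: scale.** Using the expected person counts in Section 8.7, each 10 percentage points of users wrongly left without an indication is 0.10 × 900 = 90 patients in IMASIS, 600 in IPCI, 2,370 in IQVIA DA Germany, 2,450 in SIDIAP and 5,210 in CPRD GOLD. The 10 points are a unit of scale, not an estimate.

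**Step 6: does another planned output recover the loss?** The large-scale characterisation covers days -365 to -1. The report shows the ten most frequent conditions, and the Shiny App shows those above 1%. These are aggregate frequencies: they can reveal missed diagnoses but cannot move a patient into the right stratum. Output Tables 4 to 7 in Section 8.8.4 do not mention indication strata.

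**The case against.** The window is a deliberate choice, stated consistently, and it protects against a real problem. Table S2 uses all haemolytic anaemia for the refractory autoimmune form, thrombocytopenic purpura for the refractory idiopathic form, and transplantation with its descendants. A short window is the only stated guard against unrelated codes in these sets. This stands, and it is a reason to keep [-90,+30].

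A reader might infer that the indication should instead be searched at any time before the index date. The documents do not support that as the main definition. Only 365 days of history is guaranteed, and observation starts in 2005 in SIDIAP and 2008 in IPCI (Section 8.7), while IMASIS holds patients from 1990 (Section 8.2). Look-back would differ by database and calendar year, and with broad code sets old unrelated codes would be counted as the reason for treatment.

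The capture percentages rest wholly on assumed coding rates. The index date is itself a prescribing contact, so coding may be denser around it and capture better than the constant-rate model suggests. The documents also do not say how long after diagnosis azathioprine is started; steroid-sparing use only suggests a delay. These objections stand against any claim about size, not against the mechanism.

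Section 8.6.3 plans the large-scale characterisation per indication, and its list includes the residual category, so a large failure could become visible in the app. That is a partial safeguard: it may detect the problem but does not correct the tables.

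**Conclusion.** The point holds as an untested choice whose main risk the protocol leaves unstated. A single code-based window of 121 days sends chronic disease coded earlier, and not re-coded, to the residual category. Section 11 judges misclassification probably minimal on the strength of false positives alone.

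The size is unknown. The illustrative capture of 28% to 73% at one to four codes a year, and 98% at monthly coding, depends on rates that the documents do not give. A reader might take it as an estimate of how many indications will be lost; it is not one, and the true share cannot be computed from the protocol.

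A reader might also infer that all four objectives are compromised. Overall age, sex, large-scale characterisation and treatment duration do not use the indication window and are unaffected. What is exposed is objective 2 and the per-indication strata of objectives 1, 3 and 4.

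**What to change.** 1. In Section 8.6.3 and Tables 7 and 9, keep [-90,+30] and pre-specify a parallel fixed window [-365,+30]. The required 365 days of history supports its look-back equally for every patient in every database.
2. Report under both windows the percentage for each indication, the share in 'None of the above/missing', and per-indication age, sex and treatment duration (output Tables 2, 3 and 8 in Section 8.8.4).
3. An any-time-prior window may be added as a further sensitivity column only, with a note that look-back length differs by database.
4. In Section 11, state that the narrow window gives up sensitivity for specificity and may under-ascertain indications to a different degree in each database. Update checklist item 10.8 to match.

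The cost is one more window in the existing code and additional output columns. Under the wider window more patients will carry two indications, and some older codes will not be the reason for treatment. That is why the two windows should be shown side by side.

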8.7 Study size

No sample size has been calculated as this is a descriptive Drug Utilisation Study where we are interested in the characteristics of all incident cases of new users of Azathioprine in each database. Based on a preliminary feasibility assessment, the expected person counts for Azathioprine were 900 for IMASIS, 6,000 for IPCI, 23,700 for IQVIA DA Germany, 24,500 for SIDIAP and 52,100 for CPRD GOLD.

The study period is from 2000-2023 but it should be noted that not all DPs do have observations period starting from 2000 on. For IPCI, observation period starts from 2008 and for SIDIAP from 2005.

8.8 Analysis

All analyses will be conducted separately for each database, and will be carried out in a federated manner, allowing analyses to be run locally without sharing patient-level data.

Before sharing the study package, test runs of the analytics will be performed on a subset of the data sources and quality control checks will be performed. After all the tests are passed the final package will be released in a version-controlled study repository for execution against all the participating data sources.

The data partners will locally execute the analytics against the OMOP-CDM in R Studio and review and approve the default aggregated results. They will then be made available to the Principal Investigators and study team in secure online repository (Data Transfer Zone). All results will be locked and timestamped for reproducibility and transparency.

Cell counts <5 will be suppressed to comply with the database's privacy protection regulations.

The type of analysis in this study is described in [Table 10](#).

Table 10. Description of study types and type of analysis.

Study type	Study classification	Type of analysis
Patient Level DUS	Off-the-shelf	
 - Characterisation of patient-level features - Frequency and % of indication/s - Large-scale characterisation of drug use and comorbidities - Estimation of minimum, p25, median, p75, and maximum treatment duration

8.8.1 Statistical model specification and assumptions of the analytical approach considered

R-packages

We will use the R package "DrugUtilization" package to calculate the duration of interest and the *PatientProfiles* and *CohortDiagnostics* R packages to describe the characteristics of individuals initiating treatment with Azathioprine.

	D2.2.3 - Study Protocol for P3-C1-014	
	Author(s): [name], [name]	Version: V4.0
	Dissemination level: Public	

Drug exposure calculation

Drug eras are defined as follows: Exposure starts at date of the first prescription, e.g., the index date the person entered the cohort. For each prescription, the estimated duration of use is retrieved from the drug exposure table in the CDM, using the start and end date of the exposure. Subsequent prescriptions are combined into continuous exposed episodes (drug eras) using the following specifications:

Two drug eras are merged into one continuous drug era if the distance in days between end of the first era and start of the second era is ≤ 30 days. The time between the two joined eras is considered as exposed as shown in **Figure 1**, first three rows.

Gap era joint mode	Schematics	Dose in between	Cumulative dose	Cumulative time
“first”		d_1	$d_1 \cdot (x_1 + x_{12}) + d_2 \cdot x_2$	$x_1 + x_{12} + x_2$
“second”		d_2	$d_1 \cdot x_1 + d_2 \cdot (x_2 + x_{12})$	$x_1 + x_{12} + x_2$
“zero”		0	$d_1 \cdot x_1 + d_2 \cdot x_2$	$x_1 + x_{12} + x_2$
“join”	 <small>first exposure gap second exposure</small> <small>time = x_1, dose = d_1 time = x_{12} time = x_2, dose = d_2</small>	NA	$d_1 \cdot x_1 + d_2 \cdot x_2$	$x_1 + x_2$

Figure 1. Gap-era joint mode.

For each prescription, the estimated duration of use is retrieved from the drug exposure table in the CDM, using the start and end date of the exposure, and calculated as the duration of the first treatment era of the azathioprine during the study period. Treatment duration is summarized providing the minimum, p25, median, p75, and maximum treatment duration.

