8.4 Follow-up

Study participants will be followed up from the date of first exposure to Azathioprine until date of:

1) censoring or loss to follow-up, 2) end of data availability, or 3) the end date of exposure (whichever occurs first).

	D2.2.3 - Study Protocol for P3-C1-014	
	Author(s): [name], [name]	Version: V4.0
	Dissemination level: Public	

Table 4. Operational definition of time 0 (index date) and other primary time anchors.

Study population name(s)	Time Anchor Description (e.g. time 0)	Number of entries	Type of entry	Washout window	Care Setting ¹	Code Type ²	Diagnosis position	Incident with respect to...	Measurement characteristics/ validation	Source of algorithm
Individuals initiating treatment with Azathioprine (objective 1,2, 3 and 4)	Date of first treatment with Azathioprine during study period	Single entry	Incident	Any time prior to study entry date	OP	RxNorm	N/A	Exposure	N/A	N/A

¹ IP = inpatient, OP = outpatient, ED = emergency department, OT = other, n/a = not applicable

	D2.2.3 - Study Protocol for P3-C1-014	
	Author(s): [name], [name]	Version: V4.0
		Dissemination level: Public

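### Reported treatment duration is only the first continuous azathioprine episode and can err in either direction, but Section 11 warns only of overestimation

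*Protocol*

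**What the plan says.** Objective 4 (Section 7) is to "Estimate and summarise duration of treatment with azathioprine, overall, and stratified per indication". Section 8.6.3 and output Table 8 in Section 8.8.4 report this in seven groups, from under 12 months to 10 years or more, overall and per indication.

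Section 8.8.1 sets the measurement rule. Supply periods come from the recorded start and end dates of each exposure. Eras are merged "if the distance in days between end of the first era and start of the second era is ≤ 30 days", and "The time between the two joined eras is considered as exposed". The duration is then "calculated as the duration of the first treatment era of the azathioprine during the study period".

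Section 8.4 ends follow-up at the earliest of "1) censoring or loss to follow-up, 2) end of data availability, or 3) the end date of exposure (whichever occurs first". Section 8.6.3 and the time row of Table 1 in Section 7 use the same rule.

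Section 11 says that assumptions about duration "might lead to overestimating treatment duration of treatment (considering a 30-day drug gap era". It names no error in the other direction. Item 10.8 of the ENCePP checklist (Appendix II) marks sensitivity analyses as not applicable.

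Section 6 gives the reason for interest in duration: "with long-term use, portal hypertension may occur".

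**The concern.** The objective and the output table are labelled as duration of treatment, but the rule delivers the length of one uninterrupted run of recorded supply. Once a gap exceeds 30 days the clock stops for good, whether the patient stopped, refilled late, drew on stock, obtained drug in a setting the database does not see, or had a supply length recorded wrongly. Everything prescribed afterwards is left out.

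The groups of 5 to 10 years and 10 years or more matter most for a signal linked to long-term use, and truncation would thin out exactly these groups. Section 11 prepares the reader only for a figure that is too long. Someone assessing the signal could therefore read a small share in the upper groups as evidence that long-term use is rare, when part of it may come from the rule. The effect could also differ between databases for reasons unrelated to use, since Section 11 accepts that prescription recording varies between them.

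**Working it through.** The protocol states no duration, supply length or gap rate, so there is no figure to reproduce. What can be checked is the direction and possible size of the error. **All refill inputs below are assumptions.** The 30-day rule, the first-era rule and the duration groups come from Sections 8.8.1 and 8.6.3.

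**1. Limits on each direction.** Bridging adds at most 30 days per bridged gap, and the first era cannot exceed the calendar span from the first to the last recorded supply. Truncation has no such cap and can remove years.

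**2. A user who never stops.** Let *p* be the chance per refill of a recorded gap over 30 days, and *n* the whole number of prescription periods in *Y* years, n = floor(365.25 × Y / supply days). Then P(first era reaches Y years) = (1 − p)^n.

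| Supply | p | 5 years | 10 years |
|---|---|---|---|
| 90 days (n = 20; 40) | 1% | 0.99^20 = 0.82 | 0.99^40 = 0.67 |
| | 3% | 0.97^20 = 0.54 | 0.97^40 = 0.30 |
| | 5% | 0.95^20 = 0.36 | 0.95^40 = 0.13 |
| 28 days (n = 65; 130) | 2% | 0.98^65 = 0.27 | 0.98^130 = 0.07 |

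By construction the true share is 100% in every cell. For 28-day supplies and p = 2%, the median first era is ln(0.5)/ln(0.98) × 28 = 34.3 × 28 ≈ 961 days, or 2.6 years.

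**3. Both biases together.** Step 2 ignores bridged days, so a simulation (3,000 patients per scenario) included both kinds of gap: short gaps of 1–30 days, which are bridged, and long gaps of 31–90 days, which end the era. Medians for a 5-year span of use are in years.

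| Supply | Short gaps, share of refills | Long gaps, share of refills | First era | All eras | Supplied days | First era below supplied days |
|---|---|---|---|---|---|---|
| 30 days | 50% | 0% | 5.03 | 5.03 | 4.02 | 0% of patients |
| 30 days | 30% | 2% | 3.20 | 4.89 | 4.27 | 59% |
| 30 days | 30% | 5% | 1.34 | 4.66 | 4.02 | 88% |
| 90 days | 30% | 2% | 5.07 | 5.07 | 4.93 | 30% |
| 90 days | 30% | 5% | 3.68 | 4.99 | 4.68 | 60% |

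For a 1-year span, the first era exceeded supplied days in most patients in nearly every scenario. The exception was 30-day supplies with long gaps at 10% of refills, where 46% were above and 54% below.

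**4. Reading.** The sign depends on how often gaps exceed 30 days, on supply length and on duration of use. With short use or only short gaps, the rule overestimates, as Section 11 says. With years of use and recurring long gaps, it underestimates, and the shortfall can be large.

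**The case against.** First-episode duration in new users is a legitimate descriptive measure. The rule is pre-specified and fits single incident entry and follow-up that stops at the end of exposure. The study gives context for a signal and does not relate exposure to an outcome. Section 11 is hedged and correct as far as it goes: counting bridged days as exposed can only lengthen an era. All of this stands.

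The illustration in step 2 is also favourable to the concern. It treats every gap as a recording artefact, although some gaps are true interruptions at which a continuous episode should end. It omits bridged days, and the same p per refill means far more gaps with short supplies: p = 5% with 28-day supplies would give 1 − 0.95^13 = 49% of uninterrupted users a long gap each year, which nothing in the protocol supports. This too stands, and it is why step 3 is needed and why only ranges are given.

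A reader might go further and infer that the plan mainly underestimates duration, or that Section 11 has the direction wrong. The documents do not support either. They contain no refill or supply data, and the direction reverses under plausible inputs.

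The objection does not remove the mismatch between label and measure, or the one-sided warning. A separate analysis plan might add sensitivity analyses, but the protocol's own checklist marks them as not applicable.

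**Conclusion.** The point holds in a limited form. The protocol measures the first continuous episode, reports it as treatment duration up to 10 years or more, and warns of only one of the two directions in which it can err. Section 11 is incomplete rather than false.

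The possible size is large but rests on assumptions. For uninterrupted users with 90-day prescriptions and a 1% to 5% chance per refill of a recorded gap over 30 days, 67% down to 13% would be recorded as reaching 10 years. With no long gaps, half of refills followed by a short gap and 30-day supplies, the same rule gives 5.03 years against 4.02 supplied years. Which case is nearer the truth in each database cannot be told from the protocol. This is a worthwhile correction that does not invalidate the planned analysis, and I hold it with moderate confidence.

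**What to change.** 1. Keep the 30-day first era, but call it *first continuous episode* in output Table 8.
2. Add total exposed time summed over all eras, from index to the end of observation or data availability. State in Section 8.4, Section 8.6.3 and Table 1 (Section 7) that follow-up for this measure does not stop when the first era ends. Without that change the present stopping rule could return the first-era length again.
3. Repeat the first era with at least one longer permitted gap, for example 60 and 90 days, as a sensitivity analysis, and update checklist item 10.8.
4. Say in Section 11 that bridging can overestimate duration, by at most 30 days per bridged gap, and that truncation at the first longer gap can underestimate total time on drug. The 30-day bound covers bridging only, not wrongly recorded supply lengths or drug not taken.

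The cost is a rerun with other gap settings, one further summary, edits to the follow-up text and a few more table rows. Longer gaps will count some true interruptions as exposed, which is why they belong beside the planned result and not in its place. If no analysis is added, items 1 and 4 are still needed and cost only wording.
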